Project summary

Type 1 diabetes (T1D) is a chronic disease which requires daily calculations of food intake and insulin dose adjustment to achieve good glycaemic control and minimise the risk of developing diabetic complications. However, even when glycaemic control appears to be good, as demonstrated by average glycated haemoglobin (HbA1c), children and young people with T1D frequently experience glucose variability, with levels above and below the target range. The main cause of diurnal glucose variability is food intake, which can cause postprandial hyperglycaemia. Postprandial hyperglycemia can occur after any meal, although there is some evidence that it may be worse after breakfast. There is limited data on the occurrence and cause of this and its association with different variables, including food composition and the glycaemic load of a meal.

Methods:

This project will be a quantitative study. The study proposes to recruit 90 children and young people who have T1D and who regularly use Dexcom continuous glucose monitoring (CGM). Recruitment will be via their managing dietitian. The dietitian will be asked to provide baseline information about the participants which will include demographic data and information on clinical data, treatment and anthropometrics. Participants will be asked to provide access to Dexcom CGM data throughout the period of recording. Participants will be asked to test three breakfast meals (high glycaemic load, high glycaemic with 10g added protein and medium glycaemic load) plus a control meal (usual breakfast), repeating each meal twice in a randomized order using a Latin square randomisation. The dietitian will be asked to optimise the participants insulin doses prior to commencing test meals. Participants will be asked to complete a questionnaire for each of the postprandial test and control meal periods. This will include questions about their diabetes management, food and fluid intake in addition to questions on activities all of which took place during the three-hour postprandial period. The glycaemic response to the test and control meals will be analysed using the CGM data and the results statistically described using univariate, bivariate and multivariate analysis.

Study protocol

Full Study Title:

The Breakfast Rise, Education and Knowledge Study in Children and Young People who have Type 1 Diabetes (T1D): The BREAK study.

Short title

The BREAK study.

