Although the addition of a moderate amount of protein to a carbohydrate containing meal is recommended in international guidelines (Smart *et al.* 2018) there appears to be no evidence for this as a prevention of postprandial hyperglycaemia at breakfast. It is agreed that further research into the dietetic management of T1D is required (Smart *et al.* 2018). There is also a dearth of evidence on prevalence and management of postprandial hyperglycaemia after breakfast. Seven studies tested meals at breakfast time (Ryan *et al.* 2008; Smart *et al.* 2012; Smart *et al.* 2013; Piechowiak *et al.* 2017; Faber *et al.* 2017; Lopez *et al.* 2018) however none of the aims of these studies were to establish prevalence nor resolution of postprandial hyperglycaemia at breakfast. Only two considered diet quality at breakfast (Ryan *et al.* 2008;

Groele *et al.* 2014) and neither of these provided any evidence of how to manage postprandial hyperglycaemia after breakfast.

Conclusion

It is known that chronic hyperglycaemia causes increased risk of diabetic complications. It is possible that both glucose variability and postprandial hyperglycaemia are independent risk factors for this as well. There is some evidence that glucose variability and postprandial hyperglycaemic are common occurrence for children who have T1D. However, there is a paucity of published data on the prevalence of postprandial hyperglycaemia after breakfast in children and young people with T1D and limited evidence for the impact of glycaemic load and manipulation with protein. The need for closer examination of postprandial glucose variability to elucidate methods to reduce this, has been highlighted (Tansey *et al.* 2016). Although this applies to all meals, focusing on minimising postprandial hyperglycaemia after breakfast is paramount. This can help ensure good control through the morning and rest of the day when children are at school and actively learning (Tansey *et al.* 2016).

Aim:

To describe the distribution and dispersion of glucose variability and postprandial hyperglycaemia following test and control meals at breakfast, in children and young people with T1D, using measurements from Dexcom CGM.

Objectives:

- To determine the glucose variability diurnally, nocturnally and in the three-hour postprandial breakfast test meal period using measurement of 'time in range', 'time above range' and 'time below range'.

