- To determine the variability of glucose excursion, level and peak and the recovery time in the three-hour postprandial period.
- To describe comparisons between all the above measurements and the variables of sex, age, disease duration, BMI, HbA1c, insulin dose/sensitivity and insulin regimen.
- To describe comparisons between all the above measurements and the glycaemic load and composition of the test and control meals.

Study design

This is a quantitative study. Dexcom CGM data will be collected for the period of recording. Participants will be asked to test three breakfast meals on two occasions and submit a postprandial questionnaire after each test meal to confirm it has been tested. The postprandial period will be three hours following the end of the breakfast test meal. The test meal recipes

will be provided by the chief investigator. The dietary composition of the meals has been analysed using the Nutritics dietary analysis programme (Nutritics, 2022). The glycaemic index and load of the meals is estimated from the Nutritics programme which uses available data from the international tables of glycaemic index and glycaemic loads (Atkinson *et al.* 2008; 2021). Most foods were based on average composition across different brands. For the added fibre bread used in test meal 3, an average of three known brands was used calculated by the chief investigator. The meals will be taken in the home environment with the food provided by the families. The participants will be asked to take the test meal on a day when their CGM reading is between 4-10mmol/l and when there has been no nocturnal hypoglycaemia on the night before the planned test. The participants will act as their own control. They will be asked to complete a postprandial questionnaire for control meals as well. The control meals will be their usual breakfast of choice. The study duration, commencing with the recruitment of the first participant and ending when data has been fully described, is anticipated to be two years.

Participants

Eligibility criteria

- Children and young people aged between 5-17 years
- Diagnosis of type 1 diabetes for a minimum of one year
- On multiple daily injections (MDI) together with carbohydrate counting or Continuous Subcutaneous Insulin Infusion (CSII) using either open or closed loop systems.
- Use Dexcom continuous glucose monitoring (CGM) on a regular basis
- Have a Dexcom Clarity account and use the Clarity App

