- Regularly eats a breakfast meal before midday
- Access to internet and email

Exclusion criteria

- Prescribed anti-hyperglycaemia agents *i.e.* Glucophage (Metformin) and or antidepressants.
- Any other medical conditions that may impact on the digestion and or absorption of nutrients, including coeliac disease and gastroparesis.
- Vegans
- Allergic or intolerant to the test meals
- Experiencing difficulties with food including diagnosed eating disorders
- Currently actively taking part in another research study

Recruitment

Paediatric diabetes dietitians, working across the UK, will be enrolled to help recruit participants and become principal investigators (PI) for their site. On enrolment, the chief investigator will provide the dietitians with all the relevant participant information sheets and consent forms as well as an Excel spreadsheet for entering the baseline information. The study documentation is presented in Appendices 1-9.

Sample size

The sample size power calculation is 64. This is based on using ANOVA repeated measures, within factors with four groups and measurements (3 test meals and control) with small effect size (0.15), P value 0.05 and power 0.80 and correlation among repeated measure of 0.5. The drop rate of clinical trials is often over 40%. Therefore, the aim is to recruit 90 participants to allow for this dropout rate and meet the sample size of 64. It may be possible to recruit this number of participants. There are approximately 29,000 children and young people living in the UK with T1D (Juvenile Diabetes Research Federation (JDRF), 2018). In the first phase of this study, 12 NHS sites were enrolled, and 96 children and young people were recruited to the study.

Methodology

Baseline data

In order to make comparisons between relevant variables and glucose levels, the following baseline data will be collected from the dietitians and sent to the chief investigator, along with the artificial identifier on the Excel spreadsheet as discussed earlier at the stage of recruitment of participants:

- Parent's email address
- Sex, date of birth and recent weight and height (for calculation of BMI and BMI centile) and date of when this was taken
- Date of diagnosis of T1D
- Last four HbA1c
- Total daily insulin dose (TDD)
- Insulin: carbohydrate ratios (ICR) and Insulin Sensitivity Factor (ISF)

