- Current insulin regimen - including the type of insulin prescribed and if applicable type of insulin pump i.e. open or closed loop system.

Run-in period

At recruitment the dietitians will be asked to arrange a review of the participants insulin regimen including the insulin to carbohydrate ratio's (ICR), insulin sensitivity factor (ISF) and basal background insulin doses/rates. The dietitian will be asked to inform the chief investigator when this has taken place. Participants will be asked to commence the test meals following this.

Glucose measurement

Data on interstitial glucose will be collected via Dexcom CGM. The Dexcom CGM data will be accessed by an NHS Highland research 'Clarity Clinic' with Dexcom CLARITY® Clinic Portal (Dexcom In, San Diego, CA, USA). The chief investigator is administrator of this clinic. Once the managing dietitian has obtained each participant's consent, the participant's parent's email address will be sent to the chief investigator along with the baseline information/data as described above. The chief investigator, as administrator of the Clarity Clinic account, will then invite the participant, via email, to be added to the clinic. Once the invite has been accepted, it will stand for the period of the recording i.e. until all the test meals and questionnaires have been completed. Once the participant has submitted their last questionnaire, they will be removed from the Dexcom CLARITY® Clinic Portal. They will be removed from the clinic portal if they withdraw from the study.

Test and control meals

Following the provision of CGM data and review of the insulin regimen by the diabetes team, participants will be randomised to test each of the three test meals on two separate occasions with a control meal (usual breakfast meal) for each test meal. Randomisation will be achieved using a Latin square randomisation. The tool used for this will be <http://www.jerrydallal.com/random/randomize.htm>. Randomisation will be done in a block of four.

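### Two day-selection conditions are worded for test meals only and no starting-glucose adjustment is stated, so test-versus-control comparisons of mean glucose may partly reflect which mornings were chosen

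*Combined protocol and SAP*

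**What the plan says.** Under Study design: "The participants will be asked to take the test meal on a day when their CGM reading is between 4-10mmol/l". The same sentence requires "no nocturnal hypoglycaemia on the night before the planned test". The paragraph then turns to control meals: "They will be asked to complete a postprandial questionnaire for control meals as well". It adds only that these are the participant's usual breakfast.

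The section on test and control meals opens its food rule by naming both meal types, and the drink and activity rules follow on from it. Starting glucose and the preceding night are not mentioned there.

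The aim is "To describe the distribution and dispersion of glucose variability and postprandial hyperglycaemia following test and control meals at breakfast". One objective is "To describe comparisons between all the above measurements and the glycaemic load and composition of the test and control meals". The Sample size section rests on "ANOVA repeated measures, within factors with four groups and measurements (3 test meals and control"), so control is one of the four conditions.

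The primary outcome is mean CGM glucose over the three hours after breakfast, as a level and not as a change from the start. The Data analysis section promises univariate, bivariate and multivariate analysis but names no model or covariate. Pre-meal glucose appears among the secondary outcomes as the number and percentage in target, and as the reference level for recovery time.

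**The concern.** Participants act as their own controls, so a within-person comparison is fair only if mornings are chosen in the same way for each meal. If test meals are eaten only on mornings within 4-10 mmol/l after a night without hypoglycaemia, and control meals on any morning, starting glucose differs by meal type before anything is eaten. Some of that difference will carry into an absolute three-hour mean. The Latin square balances the order of meals. It does not balance a rule about which mornings qualify when that rule depends on the meal.

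At stake are the described test-versus-control differences in the primary outcome, and any four-condition test of the kind the trial is sized on. Outcomes measured from the starting level, such as excursion and recovery time, are built differently from the primary outcome, which has no such reference.

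**Working it through.** **1. The passages side by side.** The glucose and prior-night conditions are attached to the test meal and the planned test. The control-meal sentences in the same paragraph carry neither. The rules stated for both meal types concern food, drink and activity. The advice to pick a day without planned physical activity follows the sentence naming both meal types and may cover both, so it is left out of this point. That the CGM reading is a pre-meal one is the natural reading, but no time is given.

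**2. The plan's own figure.** Inputs from Sample size: f = 0.15, m = 4 conditions, correlation ρ = 0.5, alpha 0.05, power 0.80. Sphericity is assumed.
- Noncentrality λ = f² × N × m / (1 − ρ). At N = 64: 0.0225 × 64 × 4 / 0.5 = 11.52.
- With 3 and 63 × 3 = 189 degrees of freedom, power is 0.81.
- The smallest N reaching 0.80 is 62. Entering four groups and rounding up to a multiple of four gives the stated 64. The figure reproduces.

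**3. A scale that needs no glucose assumption.** Suppose the three test meals are equal and control is displaced by b SD through day selection alone.
- The SD of the four means is b√3/4, so f² = 3b²/16.
- λ = (3b²/16) × 64 × 4 / 0.5 = 96b².

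| Control shift b (SD) | λ | Chance of a significant F test |
|---|---|---|
| 0 | 0 | 5% |
| 0.1 | 0.96 | 11% |
| 0.2 | 3.84 | 34% |
| 0.3 | 8.64 | 68% |
| 0.35 (equivalent to f = 0.15) | 11.52 | 81% |

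**4. Could day selection produce such a shift?** Every input here is assumed, because the documents give none. Pre-meal glucose is taken as normal with total SD 3 mmol/l, of which 1.5 is between participants. Compliance is full, and the night condition is not modelled.
- Selection acts within each participant, so the relevant SD is s = √(9 − 2.25) = 2.60.
- For a participant with mean μ, let a = (4 − μ)/s and c = (10 − μ)/s. The control-minus-test shift in starting glucose is s[φ(c) − φ(a)] / [Φ(c) − Φ(a)], averaged over participants.
- Between 25% and 75% of the shift is assumed to carry through to the three-hour mean.

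| Overall pre-meal mean (mmol/l) | Shift in start (mmol/l) | Shift in three-hour mean (mmol/l) |
|---|---|---|
| 7 | 0 | 0 |
| 8 | 0.65 | 0.16 to 0.49 |
| 9 | 1.32 | 0.33 to 0.99 |
| 10 | 2.01 | 0.50 to 1.51 |

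At a mean of 6.5 the shift in start is about −0.3, so the direction reverses. Truncating the pooled distribution instead, which ignores that selection is within person, gives larger shifts of 0.71, 1.43 and 2.17 at means 8, 9 and 10.

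Taking an outcome SD of 2.5 mmol/l (also assumed) and 50% carry-through:
- Mean 8: 0.326 / 2.5 = 0.13 SD, and the F test is significant about 16% of the time.
- Mean 9: 0.66 / 2.5 = 0.264 SD, and it is significant about 56% of the time.

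**The case against.** The strongest reply is that the plan uses test meal inclusively in several places. Study design defines the three-hour window by the end of the test meal, yet every postprandial outcome uses that window. The first objective refers to the test meal period under an aim that covers both meal types. Run-in period has participants start the test meals after the insulin review, although control meals share the randomised order. Appendix 11 holds the meal instructions and Appendix 10 the questionnaire, and either may extend the conditions to control days. This stands. A reader might infer that control mornings are definitely exempt, or that every day condition differs by meal type. The text does not establish either. It leaves the matter open for two conditions.

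Second, the questions stressed under Expected outcomes (high against medium glycaemic load, and added protein) are contrasts among the three test meals, which share the same conditions. This also stands, and it would be wrong to infer that those contrasts are biased.

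Third, the control is a free-choice breakfast, so test-versus-control is never a single-factor contrast, and the Data analysis section does not commit to the four-condition test. Both are true. But comparison with control meals is a stated objective, the trial is sized with control as a condition, and day selection adds a second, avoidable difference to the one in the meal.

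Fourth, multivariate analysis could include starting glucose, and an imbalance would show in the percentage with pre-meal glucose in target. Showing an imbalance does not correct the primary comparison, and an adjustment that is not stated cannot be relied on. The insulin review and closed-loop use may reduce the effect, by an amount the documents do not give.

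**Conclusion.** The point holds for two conditions (the glucose range and the preceding night), for test-versus-control comparisons, and for the plan as literally worded. If control mornings are unrestricted, those comparisons of three-hour mean glucose can partly reflect day selection.

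A reader might go further and infer a bias of known size that favours the test meals. The documents do not support that. Test-day glucose is lower if mornings above 10 mmol/l outnumber those below 4. Under the symmetric assumption above, the effect is nil at a pre-meal mean of 7 and reverses below it. The millimole figures, and the 16% and 56% built on them, rest wholly on assumed inputs. Only the SD scale uses the plan's own design values, and it says how much a given shift would matter, not that the shift will occur. The range runs from none to material. The change is worth making because it is cheap and the size cannot be known in advance. Confidence is medium, given the ambiguous wording and the unseen appendices.

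**What to change.** State whether the two conditions cover control mornings, and reconcile Study design, the section on test and control meals, and Appendix 11 accordingly.

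If control mornings are unrestricted:
- Prespecify that test-versus-control comparisons of mean glucose adjust for each occasion's pre-meal CGM glucose, for example as an occasion-level covariate in a mixed model with participant as a random effect.
- Add a sensitivity analysis limited to control occasions that met both conditions, because the covariate model extrapolates where control starts lie outside 4-10 mmol/l.
- Keep all control occasions for the description of usual breakfasts.
- Do not interpret a test-versus-control difference in the proportion starting in target as a meal effect.

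The cost is a little analysis work on CGM data already being collected, with no increase in sample size. The sensitivity analysis loses precision. Under the assumed pre-meal SD of 3, about 32%, 34%, 42% and 52% of mornings fall outside 4-10 mmol/l at means 7, 8, 9 and 10. With 64 participants and two control occasions each, the number implied by "plus a control meal (usual breakfast), repeating each meal twice in a randomized order using a Latin square randomisation", a mean of 8 would leave about 128 × 0.656 = 84 of 128 occasions before the night condition is applied. The later wording "with a control meal (usual breakfast meal) for each test meal" may mean more control occasions, so their number should be stated too.

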It is anticipated that new data, arising from the study, and the associated intellectual property will be owned jointly by the University of Stirling and NHS Highland with a sharing agreement.

Destruction of data

The Dexcom Clarity clinic only stores CGM data for three months. Once these data have been collected for the period of the study, the Dexcom research clinic will be closed. Any transferred data will be stored on the NHS Highland secure remote server for 10 years before being deleted. Personal data (emails addresses, artificial identifiers, dates of birth will be deleted 6-12 months after the study ends).

Definition of end of study

The study will end when all the participants have completed the test and control meals and submitted their questionnaire responses and their CGM data for the period of the meals has been exported and they have been removed from the Clarity clinic.

Expected outcomes

The aim of this study is to describe the distribution and dispersion of glucose variability and postprandial hyperglycaemia after test meals at breakfast and establish comparisons of these between variables obtained from baseline information and nutrient analysis. It is hoped this

will provide evidence of the impact of high and medium glycaemic load breakfast meals have on glycaemic response in children and young people who have T1D. It is also hoped the study will provide evidence of the impact additional protein has on glycaemic response when taken as part of a mixed high glycaemic load meal.

This will increase the knowledge of diabetes educators, patients and families and ensure diabetes education includes evidence-based information on how to minimise postprandial hyperglycaemia at breakfast time.

Dissemination of results

It is anticipated that one paper will be submitted for publication. The proposed journals for publication include:

- *Pediatric Diabetes*
- *Diabetic Medicine*
- *Diabetologia*
- *Diabetes Technology & Therapeutics*
- *Acta Diabetologica*.

Ethical considerations

This study has been reviewed and provided a favorable opinion by... *to be added when obtained*

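### The sample size of 64 is computed correctly, but its 80% power belongs to one four-meal F test and not to the protein or glycaemic-load comparison the study hopes to draw

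*Combined protocol and SAP*

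**What the plan says.** The Sample size section states that "The sample size power calculation is 64". The basis is a repeated-measures ANOVA, "within factors with four groups and measurements (3 test meals and control) with small effect size (0.15), P value 0.05 and power 0.80", with a "correlation among repeated measure of 0.5". To justify recruiting 90 it remarks that "The drop rate of clinical trials is often over 40" per cent, and says that 90 allows for this and still delivers 64.

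Under Test and control meals, participants are randomised "to test each of the three test meals on two separate occasions". The Project summary has the usual breakfast eaten twice as well, whereas Test and control meals has one control for each test meal, so the number of control breakfasts is not settled. The Sample size section does not mention repeat breakfasts.

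Test meal 2 is test meal 1 with 10 g of protein added, and test meal 3 has a medium glycaemic load. Expected outcomes hopes for evidence on high and medium load breakfasts and for "evidence of the impact additional protein has on glycaemic response" within a high-load meal.

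The Aim and Objectives are descriptive and cover test and control meals together. Data analysis names no model, contrast, handling of replicates or multiplicity rule. No SD or target difference in mmol/l is given for the primary outcome, mean three-hour glucose.

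**The concern.** A four-level F test asks whether any meal differs from any other. It does not say whether protein or load matters. The usual breakfast is freely chosen, and it alone could make the test significant while meals 1, 2 and 3 have equal means. The power quoted for the F test therefore cannot be carried over to either comparison.

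The calculation also has four values per child, while each test meal is eaten twice. Whether the 0.15 and the 0.5 describe one breakfast or the mean of two changes what the 80% means.

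At stake is whether a reader or an ethics committee can tell what protein or load effect the study could detect. Since the analysis section names no contrast, the key comparisons could also be chosen after the data are seen.

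**Working it through.** **Inputs from the Sample size section.** m = 4 measurements, f = 0.15 (read as Cohen's f), α = 0.05, ρ = 0.5, N = 64, dropout 40%, recruitment 90.

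**Assumptions, because the documents give no figure.** Correlation r_w between a child's two breakfasts of the same meal, 0.5 to 0.9; sphericity; both replicates complete; α split equally over two contrasts (0.025 each). SD means the SD of one breakfast's three-hour mean glucose.

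**1. Reproduce 64.** λ = N·m·f²/(1 − ρ) = 64 × 4 × 0.0225 / 0.5 = 11.52.
- One group: df 3 and 3 × 63 = 189, power 0.815; the smallest N for 80% is 62.
- Four groups: df 3 and 3 × 60 = 180, power 0.814; the smallest N that is a multiple of four is 64.

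The stated figure is right for the stated test.

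**2. What f = 0.15 implies for one pair.** It fixes the sum of squared deviations of the four meal means at 4 × 0.15² = 0.09 SD². A paired difference of single values has variance 2(1 − ρ) = 1 SD², so the two-sided paired t test has noncentrality d√64 = 8d on 63 df.

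| Pattern of the four means | Equation for d | d (SD) | Power, α 0.05 | Power, α 0.025 |
|---|---|---|---|---|
| The pair is equal | d = 0 | 0 | 0.05 | 0.025 |
| Evenly spaced, neighbouring pair | 5d² = 0.09 | 0.134 | 0.185 | 0.118 |
| Two against two | d² = 0.09 | 0.300 | 0.657 | 0.544 |
| One meal differs from three | 0.75d² = 0.09 | 0.346 | 0.779 | 0.682 |
| All spread between the pair | d²/2 = 0.09 | 0.424 | 0.917 | 0.861 |

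If the one differing meal is the usual breakfast, the F test keeps its full power of 0.815 while the true protein and load effects are both zero.

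**3. Replicates and the F test.** If the inputs describe single breakfasts, averaging two replaces 1 − ρ by (1 + r_w)/2 − ρ. The numerator N·m·f² is 5.76 at N = 64 and 4.86 at N = 54.

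| r_w | (1 + r_w)/2 − ρ | λ at 64 | Power at 64 | λ at 54 | Power at 54 |
|---|---|---|---|---|---|
| 0.5 | 0.25 | 23.04 | 0.987 | 19.44 | 0.968 |
| 0.75 | 0.375 | 15.36 | 0.918 | 12.96 | 0.861 |
| 0.9 | 0.45 | 12.80 | 0.857 | 10.80 | 0.785 |
| Single values | 0.50 | 11.52 | 0.815 | 9.72 | 0.736 |

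If the inputs already describe means of two breakfasts, the last row applies and replication has been counted.

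**4. Detectable pairwise difference at 80% power.** The variance of a difference between two-breakfast means is 2((1 + r_w)/2 − ρ). Solving the paired t test for d (bracketed values use α 0.025):

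| r_w | Variance (SD²) | d at 64 | d at 54 |
|---|---|---|---|
| 0.5 | 0.50 | 0.25 (0.28) | 0.27 (0.30) |
| 0.75 | 0.75 | 0.31 (0.34) | 0.34 (0.37) |
| 0.9 | 0.90 | 0.34 (0.37) | 0.37 (0.41) |
| Single values | 1.00 | 0.36 (0.39) | 0.39 (0.43) |

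**5. Completers.** 90 × (1 − 0.40) = 54, not 64. Keeping 64 of 90 means losing no more than 26/90 = 29%; 64 after a 40% loss would need 64/0.60 = 107 recruited.

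**The case against.** The strongest reply is that nothing has been miscalculated: 64 is correct for the inputs given. That stands. This is a point about what the power statement refers to.

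Second, four measurements per child is also what an analysis of each child's meal means would use, so replication may already be inside the 0.15 and the 0.5. That stands too. A reader might infer from step 3 that the plan understates its precision, but this holds only if the inputs describe single breakfasts, and the Sample size section does not say.

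Third, the Aim and Objectives are descriptive and cover all four meals, no hypothesis is declared, and the two contrasts come from what Expected outcomes hopes for. A four-meal test is a reasonable match to the objective of comparing test and control meals, so calling it the wrong test would go too far. But the study was sized by a hypothesis test, and meal 2 was built as meal 1 plus protein. If conclusions on protein and load are to be drawn, the power statement should cover them.

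Fourth, detectable differences in SD units still do not tell a clinician the size in mmol/l. That is fair; the documents give no SD from which to convert.

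**Conclusion.** The concern holds as a fault in the power statement. The stated 80% is the power of one omnibus test and describes neither comparison of interest. At f = 0.15, 64 children and single values, pairwise power can be anything from 0.05 to 0.92, depending on a pattern of means that the plan does not specify.

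A reader might infer that the trial is underpowered. The documents do not support that: replicates raise power, splitting alpha lowers it, and the net effect depends on the pattern of means and the same-meal correlation, neither of which is given. If the inputs describe single breakfasts, the plan is conservative for its own F test (0.86 to 0.99 at 64 for r_w 0.9 to 0.5).

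The completer count is a firmer point. The plan's own 40% dropout from 90 leaves 54, where the F test has power 0.74 on single values and 0.78 to 0.97 on two-breakfast means for r_w 0.9 to 0.5.

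These results assume sphericity, complete replicates, the plan's correlation of 0.5 between meals, and r_w between 0.5 and 0.9. The unsettled number of control breakfasts does not affect the two contrasts, which use test meals only.

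**What to change.** - Name meal 2 against meal 1 (protein) and meal 3 against meal 1 (load) as the planned key comparisons. Estimate them from a model that uses both replicates, with alpha split over the two. Keep the comparisons with the control meal as the Aim and Objectives plan them.
- State whether f = 0.15 and the correlation of 0.5 refer to one breakfast or to the mean of two.
- Restate the sample-size paragraph as detectable differences with the assumption beside them. For inputs on single breakfasts, same-meal correlation 0.5 to 0.9 and between-meal correlation 0.5, 80% power is reached for about 0.25 to 0.34 SD at 64 completers (0.28 to 0.37 with split alpha), and about 0.27 to 0.37 SD at 54 (0.30 to 0.41). If the sponsor holds an SD in mmol/l, give the differences in those units too.
- State that 40% dropout from 90 leaves 54, not 64.

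The cost is one rewritten paragraph and a few lines under Data analysis; this point by itself asks for no extra participants. The downside is that the power claim becomes specific to each contrast, rests on an assumed replicate correlation, and is slightly less favourable once alpha is split.

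### Recruiting 90 does not leave 64 at the 40% dropout the plan assumes: it leaves 54, with power of about 0.74 rather than 0.81 on the plan's own inputs

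*Combined protocol and SAP*

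**What the plan says.** The Sample size section states the requirement: "The sample size power calculation is 64". It bases this on a within-factors repeated-measures ANOVA over four conditions (the three test meals and the control), with effect size 0.15, significance level 0.05, power 0.80 and a correlation of 0.5 between repeated measures.

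On losses it says "The drop rate of clinical trials is often over 40" per cent, and draws the recruitment target from that: "Therefore, the aim is to recruit 90 participants to allow for this dropout rate and meet the sample size of 64".

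The Methods part of the Project summary repeats the target: "The study proposes to recruit 90 children and young people who have T1D". The Sample size section also reports that the first phase recruited 96 participants at 12 sites, but not how many of them completed. No section gives a lower dropout rate, a different way of inflating the sample, or a rule for replacing those who leave.

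**The concern.** The requirement of 64, the dropout of 40% or more and the target of 90 cannot all stand. To end with 64 after losing a fraction d, one divides by (1 − d). The target of 90 looks like 64 multiplied by (1 + d) instead, which undershoots. The plan shows no formula, so this is an inference from how closely the numbers match.

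This paragraph is the only justification for how many children and young people are recruited. It tells an ethics committee, funder or journal that the four-meal comparison keeps its planned size under the dropout the plan itself expects. It does not.

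**Working it through.** **Inputs, all from the Sample size section.** Effect size f = 0.15 (read as Cohen's f), α = 0.05, m = 4 measurements, correlation ρ = 0.5, target power 0.80, required N = 64, recruits = 90, dropout d = 0.40. Because the text says over 40%, taking exactly 40% favours the plan. Sphericity is not mentioned and is assumed.

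**Step 1: reproduce the 64.** The F test for a within factor has

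- noncentrality λ = f² × N × m/(1 − ρ) = 0.0225 × N × 4/0.5 = 0.18N
- df1 = m − 1 = 3
- df2 = 3(N − 1)

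The smallest N with power of at least 0.80 is 62 (power 0.801). At N = 64, λ = 11.52, df2 = 189 and power is 0.815. Entering four groups, as the plan's wording might suggest, again gives a minimum of 62, which becomes 64 when rounded up to a multiple of four; power at 64 is then 0.814. The 64 is sound on its inputs.

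**Step 2: the dropout allowance.**

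- Completers from 90 at 40% dropout: 90 × 0.60 = 54, and 64 − 54 = 10 short.
- Recruits needed for 64 completers: 64/0.60 = 106.7, so 107.
- Likely origin of 90: 64 × 1.4 = 89.6.
- Dropout that 90 can absorb: 90 − 64 = 26, and 26/90 = 28.9%. One more loss (27, or 30.0%) leaves 63.

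**Step 3: power at the numbers that remain (one value per meal).**

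| Dropout from 90 | Completers | λ = 0.18N | Power |
|---|---|---|---|
| 28.9% | 64 | 11.52 | 0.815 |
| 40% | 54 | 9.72 | 0.736 |
| 45% (assumed) | 49 | 8.82 | 0.688 |
| 50% (assumed) | 45 | 8.10 | 0.646 |

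With 54 completers, the smallest f detectable with power 0.80 is 0.161, against the planned 0.15. If sphericity fails, all of these figures fall: with ε = 0.8 (assumed), power is 0.66 at 54 and 0.75 at 64.

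**Step 4: the repeated meals.** The calculation counts one value per meal, but the meals are to be repeated. If the two occasions are averaged, λ is multiplied by 1/(g + (1 − g)/2), where g is the share of within-child variance that is child-by-meal interaction. The documents give no value for g, so the full range is shown for N = 54:

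| g (assumed) | Multiplier of λ | Power at 54 |
|---|---|---|
| 0 | 2.00 | 0.968 |
| 0.5 | 1.33 | 0.861 |
| 0.75 | 1.14 | 0.797 |
| 1 | 1.00 | 0.736 |

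This range takes two occasions for all four meals, control included. The documents do not settle that: the Project summary has "repeating each meal twice in a randomized order using a Latin square randomisation", while the Test and control meals section has participants take the test meals "with a control meal (usual breakfast meal) for each test meal".

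**The case against.** The strongest reply is that the power loss may not be real. One value per meal describes the plan's calculation, not the data to be collected. With averaged duplicates, power at 54 falls clearly below 0.80 only if more than about three quarters of the within-child variance is child-by-meal interaction. This stands as a limit on the power figure: 0.74 is the plan's own basis at 54, and the lower end of the duplicate range. It does not rescue the sentence, because duplicates do not turn 54 participants into 64, and the plan neither counts them nor gives the correlation needed to do so.

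The study is also mainly descriptive. The Aim and Objectives speak of describing, and the Data analysis section names no hypothesis test or success criterion. That limits the consequence. But the sponsor chose to justify the size by a powered four-meal ANOVA, and Expected outcomes hopes for evidence on glycaemic load and added protein, so the justification should be correct.

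Two smaller points are fair. Since 62 already gives power 0.801, power of 0.80 survives up to 28 dropouts (28/90 = 31.1%); that is still well below 40%. And the dropout remark is about clinical trials in general rather than an estimate for this study. Even so, the plan ties its target of 90 to that rate explicitly. Participants who complete only some meals might contribute under a mixed model, but none is specified.

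**Conclusion.** The concern holds. The headcount error (54 against 64, with 107 recruits needed) rests only on the plan's own 64, 90 and 40%. The fall in power from 0.815 to 0.736 rests further on the plan's inputs, one value per meal, and sphericity. Recovery through the repeated meals is possible but not assured. No decision rule fails. The stated size and power are wrong as written and must be corrected.

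**What to change.** Restate the end of the Sample size section along these lines:

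> *90 recruits give 64 completers only if no more than 26 (28.9%) drop out. At 40% dropout 54 complete, giving power of about 0.74 for f = 0.15 with one value per meal (sphericity assumed).*

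The plan may also report power at 54 with the two occasions of each meal averaged. It should then be given as a conditional range (0.74 to 0.97), with the assumed child-by-meal share and the number of control meals stated.

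The cost is wording only, with no added participants. The power quoted for 40% dropout drops from 0.80 to about 0.74 on the one-value-per-meal basis. If the sponsor would rather keep the claim of 64 completers, it must either raise the target to 107, here and in the Project summary, or support a dropout rate of at most 28.9%, for example with retention from the first phase if that is known.
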